3.6 Procedural Timetable

Action	Day 0	Day 1	Day28	1 M	3 M	6M
Consent	X					
Hx /PE	X		X	X	X	X
Parasitology (aspirate:smear/cult)	X					
Evaluate lesion	X	X	X	X	X	X
Treatment						
Oral Miltefosine			day 1 to day 28			
IL pentamidine			days 1, 3, 5			
Adverse events (esp. GI)	X	day 1	to day 28			
Blood Glucose	X	weeks 2	and 4			
AST	X	weeks 2	and 4			
Creatinine	X	weeks 2	and 4			

“Day 0” includes the screening period.

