2.0 Study Aims and design

2.1 Aim:

The primary purpose of this study is to evaluate the cure rate of a standard course of oral miltefosine in combination with intralesional pentamidine for single lesions predominately due to *L braziliensis* in Bolivia.

A secondary purpose is to determine the tolerance of this regimen.

2.2 Design:

Open label evaluation of miltefosine (28 days) plus intralesional pentamidine (days 1, 3, 5).

After treatment, all patients will be followed for 1, 3, and 6 months.

The initial number of patients will be 30.

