3.3 Study treatments

3.3.1 Miltefosine

Miltefosine will be administered daily for 28 days as per the US Product Label:

“Administer with food to ameliorate gastrointestinal adverse reactions.

- 30 to 44 kg: one 50 mg capsule twice daily for 28 consecutive days.
- 45 kg or greater: one 50 mg capsule three times daily for 28 consecutive days.”

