3.4 Efficacy evaluation

For each lesion, the size of its ulcer will be measured at 1 month, 3 months, and 6 months after the end of therapy.

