3.5 Adverse events recording

Re Miltefosine: Adverse events especially gastrointestinal will be recorded.

Re IL pentamidine: Patients will be evaluated for local side effects (pain, itching, irritation (erythema/edema), vesicles/bullae, sterile abscesses) and the possibility of bacterial superinfection both local and disseminated to the draining lymph nodes on each day that therapy is applied. Any other subjective complaint spontaneously referred by the patient will be registered and evaluated.

In addition, pentamidine patients will be evaluated for hypoglycemia.

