3.9 Additional patients

After 30 patients have been evaluated, the cure rate and tolerance of the regimen will be analyzed. If the cure rate is close to 90%, further patients may be enrolled to better ascertain the cure rate of this regimen.

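### Scheduled adverse event recording in 3.6 stops on day 28, the last miltefosine day, and has no mark at the existing 1-, 3- and 6-month visits (minor)

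*Protocol*

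**What the plan says.** Protocol 2.1 makes tolerance the second aim: "A secondary purpose is to determine the tolerance of this regimen". Section 3.9 adds when it will be looked at: "After 30 patients have been evaluated, the cure rate and tolerance of the regimen will be analyzed".

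The treatment period is fixed in 3.3.1: "Miltefosine will be administered daily for 28 days as per the US Product Label". Pentamidine is injected on days 1, 3 and 5 (2.2, 3.3.2). Follow-up is set in 2.2: "After treatment, all patients will be followed for 1, 3, and 6 months". Section 3.4 counts those visits from the end of therapy: "the size of its ulcer will be measured at 1 month, 3 months, and 6 months after the end of therapy".

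On adverse events, 3.5 has three elements:

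- For miltefosine, "Adverse events especially gastrointestinal will be recorded", with no period stated.
- For pentamidine, a list of local effects and superinfection, checked on the days of treatment, plus an evaluation for hypoglycemia.
- At the end of the pentamidine paragraph, "Any other subjective complaint spontaneously referred by the patient will be registered and evaluated", again with no period stated.

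The timetable in 3.6 is the only place in the available text that gives adverse event recording an end. Its row "Adverse events (esp. GI" is marked at Day 0 and then from day 1 to day 28. Blood glucose, AST and creatinine are taken at Day 0 and in weeks 2 and 4.

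**The concern.** Scheduled recording closes on the day the patient takes the last miltefosine dose. Two kinds of information then have no scheduled place: events that start after treatment, and the outcome of events that are present on day 28. The second case is foreseeable, because the last laboratory tests fall at about the same time. An abnormal week-4 value would arrive just as recording closes, with no repeat test or outcome entry planned.

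What is at stake is the quality of the tolerance result. This is a matter of data collection, so a later analysis plan cannot repair it: information nobody was scheduled to ask for cannot be recovered at analysis. After day 28 the tolerance data would depend on how each history was taken and on what patients chose to mention, whereas up to day 28 they come from scheduled recording.

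**Working it through.** The plan states no figure on this point, so there is none to reproduce. The check is a row-by-row reading of 3.6 against the text sections, with some simple arithmetic.

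**1. Marks in 3.6 at the follow-up visits**

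| Row | Up to day 28 | 1 month | 3 months | 6 months | Follow-up visits marked |
|---|---|---|---|---|---|
| History/physical examination | Day 0, day 28 | X | X | X | 3 of 3 |
| Lesion evaluation | Day 0, day 1, day 28 | X | X | X | 3 of 3 |
| Adverse events | Day 0, days 1 to 28 | – | – | – | 0 of 3 |
| Glucose, AST, creatinine | Day 0, weeks 2 and 4 | – | – | – | 0 of 3 |

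The blanks are unlikely to come from the conversion of the file, because two other rows of the same table carry marks at all three visits.

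**2. Scheduled recording after the last dose of each drug**

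- Miltefosine (last dose day 28): 28 − 28 = 0 days.
- Pentamidine (last injection day 5): 28 − 5 = 23 days.

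**3. Length of the unscheduled period**

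Assume 30 days per month, counted from day 28. The visits then fall near days 58, 118 and 208. From first dose to last visit is 208 days, of which 208 − 28 = 180 (180/208 = 87%) have no scheduled adverse event recording. This describes the calendar and not the risk. Most of that time is off treatment.

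**4. Weight of a single event with 30 patients (2.2)**

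- Shift in a rate: 1/30 = 3.3 percentage points.
- Exact (Clopper-Pearson) 95% interval for 0 of 30: 0 to 1 − 0.025^(1/30) = 11.6%.
- Exact 95% interval for 1 of 30: 0.1% to 17.2%.

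These figures show how sensitive any rate in 30 patients is to one event. They do not estimate how many events the day-28 limit would miss.

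**5. What else could catch a late event**

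The miltefosine sentence and the spontaneous-complaint sentence in 3.5 are both undated. History, physical examination and lesion evaluation are planned at each follow-up visit. These give real opportunities to learn of a late event. None of them is a scheduled adverse event entry, and none requires that an event or laboratory value open on day 28 be followed to its outcome.

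**The case against.** The case on the other side is substantial, and most of it stands.

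- **Late events are not shut out.** A reader might infer from the blank cells that events after day 28 go unrecorded, or that they surface only if a patient volunteers them. The document does not support either reading. Section 3.5 has two open-ended sentences, one of them the main instruction for miltefosine, and a history at 1, 3 and 6 months is a planned inquiry. What is missing is the explicit mark, not the occasion to ask.
- **Pentamidine is reasonably covered.** The adverse event row is not confined to gastrointestinal events and continues 23 days after the last injection. Patients also live at the treatment site during treatment (3.1).
- **No late toxicity is shown to be likely.** The effects the protocol anticipates are gastrointestinal for miltefosine, and local reactions and hypoglycemia for pentamidine. Nothing in the text places their onset after treatment. The single-event arithmetic would apply to any 30-patient study.
- **An on-treatment window is a coherent choice** for describing the tolerance of a 28-day regimen.

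These points reduce the weight of the concern without removing it. Section 3.5 is open-ended while 3.6 stops at day 28, and site staff commonly work from the timetable. Even a purely on-treatment definition of tolerance needs the outcome of events that began on treatment and were unresolved at its end, and the timetable does not schedule that.

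**Conclusion.** The point holds as a minor one. Section 3.6 fixes the end of scheduled adverse event recording at the last miltefosine dose, marks 0 of 3 follow-up visits, and plans no outcome record for events or week-4 laboratory abnormalities open on day 28. Tolerance is a stated aim and the visits already exist, so the tighter schedule is worth having.

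The size of the effect cannot be estimated. The documents give no onset data, and the number of late events may be zero. It would also be wrong to infer that the trial's main conclusion is at risk: cure is assessed on lesion findings through 6 months (3.7), and the decision in 3.9 to enroll more patients depends on the cure rate.

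The conclusion rests on two assumptions: that the blank cells in 3.6 are as the sponsor wrote them, and that nothing between 4.2 and 5.4, which was not available for this review, sets a longer recording period.

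**What to change.** Make two changes in 3.6:

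1. Add an adverse event mark at the existing 1-month visit, covering the local lesion-site items listed in 3.5.
2. Add one sentence: events, and abnormal week-4 glucose, AST or creatinine values, that are open on day 28 are followed to resolution at the visits already planned.

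Leave 3.5 as it is, so that its undated sentences continue to apply. Events that first appear between the 1-month and 6-month visits would still rely on 3.5 and on the planned history and examination. That is proportionate, since nothing in the documents points to late onset. The 1-month visit is also the nearest to treatment, and patients whose lesion fails may leave the study and receive other treatment after it (3.8, 3.8.1).

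Cost: no new visit and no extra staff. For 30 patients, 30 × 1 = 30 further CRF entries, plus follow-up entries for whatever is open on day 28 and possibly some repeat tests for abnormal week-4 values. Recorded event rates may come out slightly higher.

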3.7 Efficacy response criteria (cure and failure)

A lesion will be defined as a treatment failure if:

- enlarges by 50% by 1 month after therapy
- does not diminish by 50% at 3 months after therapy
- does not completely reepithelialize by 6 months after the end of therapy.
- relapses (enlarges substantially---approximately 25%) after previously diminishing in size
- new lesion from which Leishmania can be demonstrated

Cure will be defined as complete healing of all lesions by 6 months after the end of therapy.

Thus for a patient to be cured: no lesion could enlarge by 50%, relapse, or heal incompletely; and no new Leishmania-positive lesion can have appeared.

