3.8 Early withdrawal from study

- If a lesion fails.
- If the physician or patient otherwise thinks it advisable.

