4.0 Data analysis

4.1 Primary outcome variable (cure)

Cure vs failure will be computed using the chi-square test or Fischer's exact test.

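### Section 3.7 gives a lesion that shrinks slowly but heals by 6 months two opposite primary outcomes, and does not say which prevails

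*Protocol*

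**What the plan says.** Section 3.7 of the protocol states the outcome three times.

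- **Failure list.** Five separate criteria: at 1 month the lesion "enlarges by 50% by 1 month after therapy"; at 3 months it "does not diminish by 50% at 3 months after therapy"; at 6 months it "does not completely reepithelialize by 6 months after the end of therapy"; it relapses; or a new parasite-positive lesion appears.
- **Cure definition.** "Cure will be defined as complete healing of all lesions by 6 months after the end of therapy". It sets no condition at 3 months.
- **Summary sentence.** "Thus for a patient to be cured: no lesion could enlarge by 50%, relapse, or heal incompletely"; it goes on to exclude any new positive lesion.

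Three other sections bear on how a patient is scored. Section 3.8 gives "If a lesion fails" as a reason for early withdrawal, and 3.8.1 sends withdrawn patients to off-protocol treatment. Section 2.2 says "After treatment, all patients will be followed for 1, 3, and 6 months". Section 4.1 treats the primary outcome as binary: "Cure vs failure will be computed using the chi-square test" or an exact test.

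**The concern.** The cure rate is the primary purpose of the study (section 2.1), so every patient must map to exactly one of cure or failure. For one recognisable type of patient, the slow responder who nevertheless heals in time, section 3.7 gives both answers.

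The study is open label. If the rule is not settled beforehand, whoever scores such a patient chooses between the two readings after seeing the result. The same cure rate feeds the decision in section 3.9, where further enrolment may follow if the rate among the first 30 patients is near 90%.

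**Working it through.** The protocol derives no figure on this point, so there is none to reproduce. The check is first one of logic, then of size.

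**1. The three statements side by side**

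| Event | Failure list | Cure definition | Summary sentence |
|---|---|---|---|
| 50% enlargement at 1 month | failure | not addressed | bars cure |
| Less than 50% reduction at 3 months | failure | not addressed | not addressed |
| Not healed by 6 months | failure | bars cure | bars cure |
| Relapse | failure | not addressed | bars cure |
| New positive lesion | failure | not addressed if healed by 6 months | bars cure |

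The summary sentence carries over four of the five criteria. Only the 3-month criterion appears nowhere outside the list.

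**2. All possible patients**

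Five yes/no criteria give 2^5 = 32 combinations. Healing by 6 months occurs in 16 of them, and 15 of those 16 meet at least one other failure criterion.

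- In 14 of the 15, the list conflicts only with the bare cure definition, and the summary sentence settles the matter as not cured.
- In exactly one, the list says failure while both the cure definition and the summary sentence say cure: less than 50% reduction at 3 months, healed by 6 months, with no 50% enlargement, relapse or new lesion.

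A lesion 40% smaller at 3 months and healed at 6 months is an example of that one combination.

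**3. Size**

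Input: n = 30 (section 2.2). One patient changes the rate by 1/30 = 0.033, or 3.3 percentage points.

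The number of such patients is not in the protocol. Assume, for illustration, that 27 of 30 are cured when slow healers count as cures, and that 0 to 3 of those are rescored. Exact (Clopper-Pearson) 95% limits for x cures in n are the 2.5% point of Beta(x, n − x + 1) and the 97.5% point of Beta(x + 1, n − x).

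| Rescored | Cures | Rate | 95% CI |
|---|---|---|---|
| 0 | 27/30 | 90.0% | 73.5 to 97.9 |
| 1 | 26/30 | 86.7% | 69.3 to 96.2 |
| 2 | 25/30 | 83.3% | 65.3 to 94.4 |
| 3 | 24/30 | 80.0% | 61.4 to 92.3 |

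In this illustration, rescoring a single patient takes the lower limit from above to below the roughly 70% that sections 1.1 and 1.2 give for existing treatments. The protocol sets no test against 70%, so this shows sensitivity and is not a changed decision.

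**The case against.** The best reply is that the text can be read consistently. The failure list is categorical, section 4.1 treats cure and failure as complements, and section 3.8 withdraws a patient once a lesion fails. On that reading a 3-month failure is final, and the summary sentence is only a loose paraphrase whose reference to incomplete healing covers both inadequate-healing criteria. It can also be said that the scoring of withdrawn patients belongs in a statistical analysis plan, that the number affected is unknown, and that the 90% threshold in section 3.9 is discretionary.

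Part of this stands. The list together with section 3.8 is the more consistent reading, the size shown is illustrative, and no fixed decision can be shown to flip. The rest does not remove the conflict:

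- The cure definition immediately before the summary sentence ties healing to 6 months. A lesion fully healed by then has not healed incompletely.
- Section 3.8 governs withdrawal and does not say how the patient is scored. Section 2.2 has all patients followed to 6 months, so a later result may exist. A patient who heals by 6 months after off-protocol treatment would still meet the literal cure definition.
- A statistical analysis plan could choose one reading, but only by overriding a sentence of the protocol. The point concerns definitions the protocol does state and that disagree.

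**Conclusion.** The concern holds. The primary outcome is wrong as written: one definable type of patient is a failure under the list in section 3.7 and a cure under both the definition and the summary that follow it, with no stated order of precedence. The effect is 3.3 percentage points per affected patient at n = 30. How many patients are affected cannot be known from the protocol and may be zero; the shift from 90.0% to 80.0% rests on an assumed starting count of 27 and an assumed three slow healers. The logical conflict depends on neither assumption. It must be fixed because it sits in the definition of the primary endpoint.

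**What to change.** Reconcile the failure list, the cure definition and the summary sentence in section 3.7 with section 3.8, so that each patient has one outcome. The version closest to the list and section 3.8 would:

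1. add the 3-month criterion to the summary sentence; and
2. state that, for scoring the endpoint only, a patient who meets any failure criterion remains a failure even if the lesion later heals, including after off-protocol treatment.

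This concerns scoring alone and leaves untouched when a patient is withdrawn or how the patient is treated. If the other reading is intended, the failure list and section 3.8 need to be aligned with it instead.

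The cost is one or two sentences, with no added visits or measurements. The downside of the version above is a possibly slightly lower reported cure rate, because slow healers would count as failures.

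A side note that carries no weight in the conclusion: while section 3.7 is open, state whether the 50% and 25% changes refer to ulcer area or diameter. For a lesion of constant shape, a 50% fall in area is a fall in diameter of 1 − √0.5 = 0.293, or about 29%.

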3.8 Early withdrawal from study

- If a lesion fails.
- If the physician or patient otherwise thinks it advisable.

3.8.1 Treatment of withdrawn patients

Withdrawn patients will be treated off-protocol with best available measures as determined by the patient's personal physician.

3.9 Additional patients

After 30 patients have been evaluated, the cure rate and tolerance of the regimen will be analyzed. If the cure rate is close to 90%, further patients may be enrolled to better ascertain the cure rate of this regimen.

4.0 Data analysis

4.1 Primary outcome variable (cure)

Cure vs failure will be computed using the chi-square test or Fischer's exact test.

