1.1 Background

Cutaneous leishmaniasis (CL) is endemic in the New World from approximately the US-Mexican border through Central America and the Northern part of South America down to the level of Rio de Janeiro.

The cure rate for New World CL is only approximately 70% for all recognized therapies. For systemic therapy with the classic agent pentavalent antimony, recent cure rates of New World CL are 50% to 75% [1-5]. For the new oral agent miltefosine in 3 of these studies, the cure rate was 57-75% [2-4]. CL can also be treated locally. For intralesional (IL) antimony, cure rates are reported as 56-75% for Iranian CL [6-7], 80-83% for *L braziliensis* in Brazil [8-9], and most recently 70% for *L braziliensis* in Bolivia when the concomitant placebo cure rate was 18% [10].

A novel approach was to evaluate intralesional pentamidine for Bolivian CL. The rationale for IL pentamidine is that little drug is administered via intralesional injection, thus the toxicity of systemic pentamidine would be unlikely to be seen. For Bolivian CL, 3-injections of IL Pentamidine over 5 days cured 72% of patients whereas 3-injections of IL antimony over 5 days cured 57% [manuscript submitted]. Adverse effects were local irritation and injection site pain: IL pentamidine (30 patients)—mild (4 patients), moderate (3); IL antimony (60 patients)—mild (25 patients), moderate (4). No pentamidine patient experienced the side effects of systemic pentamidine administration: sterile abscess, hypotension, or hypoglycemia. We concluded that IL pentamidine is an attractive alternative to standard intralesional antimony for Bolivian *Leishmania braziliensis* on the basis of efficacy, the threat of antimony-resistant parasites, tolerance, and patient convenience of 3 visits over 5 days.

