1.2 Rationale

Although patients can be treated with one of these agent with the anticipation of an approximately 70% cure rate, and failures of the first treatment could then be treated with another agent, an initial cure rate > 70% would be desirable.

We propose to evaluate oral miltefosine plus intralesional pentamidine for Bolivian CL. Efficacy should be additive, since the postulated mechanisms of the drugs is different. The structure of miltefosine is similar to that of phosphatidylcholine, and may interfere with phosphatidylcholine biosynthesis or function[11]. In contrast, it is thought that pentamidine interferes with polyamine biosynthesis [12]. The advantage of the combination of oral miltefosine and IL pentamidine vs other possible drug combinations is that the systemic partner is oral rather than parenteral, and that the intralesional partner is the most active of the IL agents that we have found in Bolivia. The combination should be well tolerated, since the local side effects of pentamidine would not interact with the systemic gastrointestinal side effects of miltefosine. Finally, this combination would be

convenient, since intralesional injections of pentamidine would occur on days 1, 3, and 5 of the standard 28-day miltefosine treatment course when patients are already under medical care.

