5.5 Ethical review

The protocol will be approved by the responsible ethical committee as an extension of the IL pentostam/ IL pentamidine protocol.

The protocol will be listed on www.ClinicalTrials.Gov.

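### Section 4.1 fixes a chi-square or Fisher test as the primary analysis of a one-arm trial without designating a comparator, and does not name the cure-rate estimate that the aim asks for

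*Protocol*

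**What the plan says.** Section 2.1 gives the aim: "The primary purpose of this study is to evaluate the cure rate of a standard course of oral miltefosine in combination with intralesional pentamidine". Section 2.2 describes a single open-label regimen given to 30 patients initially, with no control arm.

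Section 4.1 is one sentence: "Cure vs failure will be computed using the chi-square test or Fischer's exact test". It gives no second group, reference rate, significance level, proportion or interval.

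Other sections contain figures that could serve as a reference, but none is linked to the test:

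- Section 1.1 puts recognized therapies at about 70%. It also reports 72% cured with IL pentamidine and 57% with IL antimony in earlier Bolivian patients.
- Section 1.2 says "an initial cure rate > 70% would be desirable".
- Section 3.9 says that the cure rate will be analyzed after 30 patients, and adds: "If the cure rate is close to 90%, further patients may be enrolled to better ascertain the cure rate of this regimen".
- Section 5.5 has the protocol approved "as an extension of the IL pentostam/ IL pentamidine protocol". That sentence concerns ethical approval. It does not make the earlier patients a control group.

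**The concern.** Cure and failure are the two values of one outcome in the same patients (section 3.7). They are not two groups, so a test that compares groups has nothing to compare. The aim, and the wording of 3.9 about ascertaining the cure rate better, call for estimation. The only method that 4.1 fixes yields neither a rate nor an interval.

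To carry out 4.1 at all, the analyst must supply a comparator or a null rate. The protocol offers several candidates and chooses none, so the choice could be made once the cure count is known. In an open-label trial of 30 patients, that choice can decide whether a result is called significant.

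**Working it through.** The protocol states no hypothesis, significance level, power or sample-size derivation, so it has no figure of its own to reproduce. The check asks what 4.1 would produce for plausible outcomes.

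**Inputs**

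- n = 30 (section 2.2).
- Illustrative outcome 27/30 = 90%, matching the rate in 3.9.
- Second illustrative outcome 21/30 = 70%, matching the background rate in 1.1 and 1.2.
- Earlier groups: 72% and 57% (section 1.1). That section gives 30 and 60 patients only with the adverse-effect data, so the cure counts are assumptions. No count out of 30 rounds to 72% (21/30 = 70.0%, 22/30 = 73.3%), while 21/29 = 72.4%. For antimony, 34/60 = 56.7%.
- The 95% level and two-sided tests are also assumptions, except where a one-sided test is stated.

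**1. Fisher on one group.** The table with 27 cured, 3 failed and an empty second row returns p = 1 and an undefined odds ratio. It carries no information.

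**2. Fisher against an earlier group, 27/30 in this trial (two-sided)**

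| Assumed comparator | p |
|---|---|
| IL pentamidine 21/29 | 0.104 |
| IL pentamidine 22/30 | 0.181 |
| IL antimony 34/60 | 0.0016 |

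**3. One-sample chi-square.** X² = (x − np₀)²/(np₀) + (x − np₀)²/(n(1 − p₀)), 1 df.

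| Cured | p₀ | Calculation | X² | p |
|---|---|---|---|---|
| 27/30 | 0.70 | 36/21 + 36/9 | 5.71 | 0.017 |
| 27/30 | 0.75 | 20.25/22.5 + 20.25/7.5 | 3.60 | 0.058 |
| 27/30 | 0.80 | 9/24 + 9/6 | 1.87 | 0.17 |
| 21/30 | 0.50 | 36/15 + 36/15 | 4.80 | 0.028 |
| 21/30 | 0.70 | 0/21 + 0/9 | 0 | 1.00 |

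The 75% and 80% rows show sensitivity only. In section 1.1, 75% is the upper end of the ranges for systemic antimony and for miltefosine, and 80% is the lower end of the Brazilian IL antimony range. The 50% row applies if the cure and failure counts are entered with equal expected counts.

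**4. The estimate.** Clopper-Pearson 95% limits are the 0.025 quantile of Beta(x, n − x + 1) and the 0.975 quantile of Beta(x + 1, n − x).

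- 27/30 = 90%: 73.5% to 97.9%.
- 26/30 = 86.7%: 69.3% to 96.2%.
- 21/30 = 70%: 50.6% to 85.3%.

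**5. A well-defined test, if one is wanted.** Exact binomial, n = 30, p₀ = 0.70. Alpha is P(X ≥ r | 0.70) and power is P(X ≥ r | 0.90).

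- r = 26: alpha 0.030, power 0.825.
- r = 27: alpha 0.0093, power 0.647.

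At one-sided 0.025 the critical value is 27. At one-sided 0.05, 26/30 would pass although its 95% CI includes 70%.

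**The case against.** The strongest reply is that the cure rate is plainly planned, in 2.1 and 3.9, and that the type of interval may be left to a statistical analysis plan. The proportion cured does not change with the comparator, and the protocol claims no superiority, so only an attached significance statement could shift. This is fair as far as it goes. A missing interval alone would not be a finding, and it is safer to say that the result could depend on a later choice than that it must. The mismatch remains: 4.1 positively fixes a test that does not fit the design, and an analysis plan could put that right only by departing from it.

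A second reply is that about 70% is the obvious reference. It does appear in 1.1 and 1.2, and naming it would make a one-sample chi-square possible. But 4.1 does not name it, and Fisher's test would still lack a second group.

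A third reply is that some scenarios are hypothetical. The Fisher results rest on assumed counts, and nothing in the protocol proposes a 50% null. Both points are correct and are stated as assumptions here. The 70% chi-square and the exact interval do not depend on the earlier groups' counts.

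**Conclusion.** The concern holds. Of the two tests in 4.1, one cannot be run on this design and the other is undefined without a null rate that the protocol does not designate. The same 27/30 would be non-significant against one earlier group (p = 0.10 or 0.18) and clearly significant against the other (p = 0.0016). Against fixed rates, p runs from 0.017 at 70% to 0.17 at 80%. The comparisons with earlier groups rest on reconstructed counts, and the 50% null is only one possible reading of 4.1.

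This should be fixed, but it does not undermine the trial. The cure proportion and its interval can be obtained from the data already planned, and no step of conduct depends on 4.1.

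**What to change.** Replace the sentence in 4.1 with, for example: 'The primary analysis is the proportion of treated patients who are cured, as defined in section 3.7, with its exact (Clopper-Pearson) 95% confidence interval.' Pointing to 3.7 matters because cure there also requires no relapse, no 50% enlargement and no new positive lesion, not just healed status at one visit. The investigators should confirm that treated patients are the denominator they intend.

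Only if superiority to existing therapy is to be claimed, prespecify an exact one-sample binomial test against a justified reference rate, such as the roughly 70% in 1.1 and 1.2. A one-sided 0.025 level keeps it consistent with the 95% interval. Against 70% it requires at least 27 of 30, with about 65% power at a true 90%. Accepting 26 of 30 raises power to about 82% at an alpha of 0.030, but loses that consistency. Do the test once, on the first 30 patients.

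If 3.9 leads to more enrolment, report the interval for the first 30 and for all patients. Note that the pooled figure is selected upward, because enrolment continues only after a high early rate. Label any comparison with the earlier IL pentamidine or IL antimony patients as exploratory and non-concurrent.

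The cost is a wording change in 4.1, with no extra patients, visits or data.
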